2. Be aged ≥ 18 years on the date of signing the informed consent form.
3. Have relapsed or refractory CD20-positive B-cell NHL that, in the investigator's opinion, could benefit from MT-3724+LEN therapy. Subjects must have proof of CD20-positive NHL, either by:
 - a. Historical biopsies (obtained with diagnosis of relapsed or refractory disease), or
 - b. Fresh biopsies.
 - c. Bone marrow biopsy, excisional lymph node biopsy, or core biopsy of any involved organ are all acceptable methods; fine needle aspirates (FNA) are not acceptable.
4. All subtypes of B-cell NHL may be considered for Part 1 (MT-3724 Dose Escalation). Only histologically documented DLBCL (including mixed histology) may be considered for Part 2 (MTD Expansion Cohort).
5. Have received all available approved therapies for NHL, one of which should be anti-CD20-based therapy.
 - a. Subjects whose prior therapy includes chimeric antigen receptor T-cell (CAR-T) therapy are eligible.
 - b. Subjects who underwent stem cell transplant (SCT) >100 days for autologous SCT or >180 days for allogeneic SCT before study drug administration and exhibited a full hematological recovery (consistent with the existing inclusion criteria requirements and without PRBC or platelet transfusions within 2 weeks of C1D1) prior to relapse are eligible.
 - c. Subjects who have been ineligible for approved therapies in the opinion of the investigator, or have refused such therapies, may be eligible at the investigator's discretion, upon sponsor approval.
6. Have bi-dimensionally measurable disease by Lugano Classification for NHL:
 - a. >1.5 centimeter (cm) longest diameter (LDi) for lymph nodes
 - b. >1.0 cm LDi for extra nodal disease
7. Have Eastern Cooperative Oncology Group (ECOG) performance status of ≤ 2 ([Appendix 6](#)).
8. Have adequate bone marrow function, as determined by all the following:
 - a. Absolute neutrophil count (ANC) $\geq 1,000/\text{mm}^3$ and
 - b. Platelet count $\geq 50,000 \text{ mm}^3$
 - c. Hemoglobin $\geq 8\text{g/dL}$
9. Have adequate kidney function, creatinine clearance (CLcr) to be $\geq 50\text{mL/min}$ either measured or assessed by using the Cockcroft-Gault formula ([Appendix 5](#)).

- a. At the investigator's discretion, the eGFR result ≤ 50 mL/min may be verified by measurement of CLcr based on the 24-hour urine collection. Subjects with CLcr ≥ 50 mL/min will be eligible irrespective of the eGFR result.
10. Have adequate hepatic function, as determined by:

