All subjects who receive at least one dose of MT-3724 or LEN will be included in the safety analysis set, the analysis of tumor response and PD analysis set. All safety and tolerability evaluations will be based on this analysis set.

All subjects who received at least one dose of MT-3724 or LEN and have at least one post-treatment PK and immunogenicity assessment will be included in the analysis set for the PK and immunogenicity analysis, respectively. The subjects who received only LEN will be excluded from the PK and immunogenicity analysis.

Safety Analyses

Adverse events (AEs), serious adverse events (SAEs) and medical history findings will be coded according to MedDRA dictionary and graded for severity using the CTCAE v5.0. The AEs and SAEs are treatment-emergent if they have started or worsened after the start of the first dose of MT-3724.

Descriptive summary tables will present the number of subjects [n], mean, standard deviation, median, minimum and maximum for continuous variables and number of subjects [n] and percent for categorical variables).

Efficacy Analyses

The investigator at each site will determine the objective tumor response (OR) at each time point based on the radiologist's measurement of tumor lesions and using the five-point scale (5PS) per the Lugano Classification for Lymphoma ([Cheson 2014](#)) adjusted according to LYRIC (lymphoma response to immunomodulatory therapy criteria) ([Cheson 2016](#)) ([Appendix 3](#)). The best overall response rate (BORR) of all time points will be reported. Subjects who experience disease progression before undergoing the first tumor assessment will be added to the disease progression stratum. The best overall response rate (BORR) will

be descriptively summarized by the treatment group/cohort; the exact 95% confidence intervals will also be produced.

The OR representing clinically significant clinical benefit in this study will comprise the Lugano Score 1, 2 or 3 or the complete response (CR) or partial response (PR). All subjects achieving clinically significant clinical benefit according to both response criteria will be included in the analysis of the duration of tumor response (DOR). DOR is defined as the time from the first documented CR or PR to the actual date of disease progression or death before progression. The DOR will be descriptively summarized by the treatment group/cohort; the exact 95% confidence intervals will also be produced.

Pharmacokinetic Analyses

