6.6 Efficacy assessments: Radiological Assessment of Tumor Response

The tumor response assessment should be performed at the following time points:

- At Screening:
 - The investigator is encouraged to obtain the screening tumor scan as close as possible to the start of treatment within 28 days of C1D1.
- Within 7 days before the start of treatment on C3D1 and every other cycle thereafter (i.e. Between D23 and D28 of the cycle). The original schedule needs to be maintained even if there is a delay in dosing.
- Within 7 days of the EoT Visit (**only** if the previous tumor scan has been performed >4 weeks before the EoT Visit)

The investigator and the radiologist should carefully consider if the increase from baseline in tumor size could be “pseudoprogression” due to the tumor flare induced by the study drug(s).

Unscheduled tumor response assessment by FDG-PET-CT (or CT/MRI, where applicable) may be ordered at the investigator’s discretion.

Efficacy of the study drugs (tumor response) will be assessed by the scan of all anatomic regions involved with the measurable disease. Positron emission tomography-computed tomography should be used in subjects with FDG-avid tumor histology. Computed tomography or MRI should be used in subjects with tumor histology of low or variable FDG avidity. Diagnostic quality CT should be collected for all subjects at baseline, whenever possible.

Tumor response in subjects with FDG-avid tumor histology will be determined using the 5-point scale (5PS) according to the Lugano Classification for Lymphoma ([Cheson 2014](#)) adjusted according to LYRIC (lymphoma response to immunomodulatory therapy criteria) ([Cheson 2016](#)). An overview of NHL response criteria for FDG avid and non-avid NHL is presented in [Appendix 3](#).

The same technique (e.g. slice thickness, field of view) should be used for all scans during the study treatment period. Preferably, all scans should be interpreted by the same investigator during the study whenever possible. Scans must meet the SOC for imaging of lesions in the respective organ system(s).

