7.9 Efficacy analyses

The statistical analysis of efficacy variables will be performed on the safety population.

Tumor assessment will be performed by the FDG-PET-CT scan in subjects with FDG-avid NHL histology along with CT or MRI to capture measurements, wherever possible, and by the CT or MRI scan in subjects with low or variable FDG avidity. The investigator at each site will determine the ORR at each time point based on the radiologist's measurement of all evaluable lesions.

The investigator at each site will determine the objective tumor response (OR) using the 5PS per the Lugano Classification for Lymphoma ([Cheson 2014](#)) adjusted according to LYRIC (lymphoma response to immunomodulatory therapy criteria) ([Cheson 2016](#)). An overview of LYRIC is presented in [Appendix 3](#). The BORR of all time points will be reported. Subjects

who experience disease progression before undergoing the first tumor assessment will be added to the disease progression stratum. The BORR will be descriptively summarized by the treatment group/cohort; the exact 95% confidence intervals will also be produced.

The ORR representing clinically significant clinical benefit in this study will comprise the Lugano Score 1, 2 or 3, or the CR or PR. All subjects achieving clinically significant clinical benefit according to both response criteria will be included in the analysis of the DOR. DOR is defined as the time from the first documented complete or partial response to the actual date of disease progression or death before progression. The PFS will be defined as the time from the start of treatment with MT-3724 on C1D1 to the date of disease progression or death from any cause. Subjects who have not progressed or died at the time of data base lock will be censored at the date of their last tumor assessment. The DOR will be descriptively summarized by the treatment group/cohort; the exact 95% confidence intervals will also be produced.

The DCR will be defined as the percent of subjects with objective response of CR, PR or stable disease (SD, defined as SD for 6 months or longer). The DCR will be analyzed using similar methods as the ORR. Further details will be provided in the SAP.

A detailed description of analysis methods will be provided in the SAP to be completed before the EoT Visit in the last subject.

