Response and Site	PET-CT-Based Response	CT/MRI-Based Response
Complete	Complete metabolic response	Complete radiologic response (all of the following)
Lymph nodes and extralymphatic sites	5PS score of 1, 2, or 3 ¹ with or without residual mass. It is recognized that in Waldeyer's ring or extranodal sites with high physiologic uptake or with activation within spleen or marrow (e.g., with chemotherapy or myeloid colony-stimulating factors), uptake may be greater than normal mediastinum and/or liver. In this circumstance, complete metabolic response may be inferred if uptake at sites of initial involvement is no greater than surrounding normal tissue even if the tissue has high physiologic uptake	Target nodes/nodal masses must regress to ≤ 1.5 cm in LD _i No extralymphatic sites of disease
Nonmeasured lesion	Not applicable	Absent
Organ enlargement	Not applicable	Regress to normal
New lesion(s)	None	None
Bone Marrow	No evidence of FDG-avid disease in marrow	Normal by morphology; if indeterminate, IHC negative
Partial	Partial metabolic response	Partial remission (all of the following)
Lymph nodes and extralymphatic sites	Score 4 or 5 on the 5PS (Table 13) with reduced uptake compared with baseline and residual mass(es) of any size. At interim, these findings suggest responding disease. At end of treatment, these findings indicate residual disease	$\geq 50\%$ decrease in SPD of up to 6 target measurable nodes and extranodal sites When a lesion is too small to measure on CT, assign 5 mm x 5 mm as the default value When no longer visible, 0 x 0 mm For a node >5 mm x 5 mm, but smaller than normal, use actual measurement for calculation
Nonmeasured lesion	Not applicable	Absent/normal, regressed, but no increase
Organ enlargement	Not applicable	Spleen must have regressed by $>50\%$ in length beyond normal
New lesion(s)	None	None

Bone Marrow	Residual uptake higher than uptake in normal marrow but reduced compared with baseline (diffuse uptake compatible with reactive changes from chemotherapy allowed). If there are persistent focal changes in the marrow in the context of a nodal response, consideration should be given to further evaluation with MRI or biopsy or an interval scan	Not applicable
No response or stable disease	No metabolic response	Stable disease

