Target nodes/nodal masses, extranodal lesions	Score 4 or 5 with no significant change in FDG uptake from baseline at interim or end of treatment	<50% decrease from baseline in SPD of up to 6 dominant, measurable nodes and extranodal sites; no criteria for progressive disease are met
Nonmeasured lesion	Not applicable	No increase consistent with progression
Organ enlargement	Not applicable	No increase consistent with progression
New lesion(s)	None	None
Bone Marrow	No changes from baseline	Not applicable
Progressive Disease	Progressive metabolic disease	Progressive disease requires at least 1 of the following
Individual target nodes/nodal masses Extranodal lesions	Score 4 or 5 with an increase in intensity of uptake from baseline and/or New FDG-avid foci consistent with lymphoma at interim or end-of-treatment assessment	An individual node/lesion must be abnormal with: LDi >1.5 cm and Increase by ≥50% from PPD nadir and An increase in LDi or SDi from nadir: 0.5 cm for lesions ≤2 cm 1.0 cm for lesions >2 cm In the setting of splenomegaly, the splenic length must increase by >50% of the extent of its prior increase beyond baseline (e.g., a 15-cm spleen must increase to >16 cm). If no prior splenomegaly, must increase by at least 2 cm from baseline New or recurrent splenomegaly
Nonmeasured lesion	None	New or clear progression of preexisting nonmeasured lesions
New lesion(s)	New FDG-avid foci consistent with lymphoma rather than another etiology (e.g., infection, inflammation). If uncertain regarding etiology of new lesions, biopsy or interval scan may be considered	Regrowth of previously resolved lesions A new node >1.5 cm in any axis A new extranodal site >1.0 cm in any axis; if <1.0 cm in any axis, its presence must be unequivocal and must be attributable to lymphoma Assessable disease of any size unequivocally attributable to lymphoma
Bone Marrow	New or recurrent FDG-avid foci	New or recurrent involvement
LYRIC Indeterminate response (IR)²	Increase in FDG uptake without a concomitant increase in lesion size meeting criteria for PD	>50% increase in SPD in first 12 weeks <50% increase in SPD with a. New lesion(s), or

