6.1.1 Objective Response Rate

The ORR measures the proportion of subjects with a reduction in tumor size (Partial Response or Complete Response) using the five-point scale (5PS) per the Lugano Classification for Lymphoma (2) adjusted according to LYRIC (lymphoma response to immunomodulatory therapy criteria) (3). An overview of LYRIC is presented in the protocol. The proportion of subjects with a Partial Response or Complete Response will be summarized and presented at each scheduled visit. The ORR representing clinically significant clinical benefit in this study will comprise the Lugano Score 1, 2 or 3, or the CR, CRu or PR. The number and percentage of subjects with clinically significant results will be presented.

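### A follow-up PET score of 1-3 counts as response whatever the baseline score, so a subject whose whole entry scan scores 1-3 is a complete responder with no change

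*Protocol*

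**What the plan says.** **Response rule.** The synopsis (Statistical Considerations, Efficacy Analyses) says: "The OR representing clinically significant clinical benefit in this study will comprise the Lugano Score 1, 2 or 3", with CR or PR as the alternative. Protocol 7.9 says that ORR "will comprise the Lugano Score 1, 2 or 3, or the CR or PR". SAP 6.1.1 says that it "will comprise the Lugano Score 1, 2 or 3, or the CR, CRu or PR". None of the three mentions the score at entry. SAP 6.1.1 also opens by describing ORR as the proportion of subjects whose tumors became smaller, and SAP section 4 gives the SAP precedence over the protocol.

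**Category definitions (Protocol Appendix 3, Table 12, PET column).**
- Complete metabolic response: "5PS score of 1, 2, or 3". A residual mass is allowed, and there must be no new lesions and no avid marrow disease.
- Partial metabolic response: a score of 4 or 5 "with reduced uptake compared with baseline and residual mass(es) of any size".
- No metabolic response: "Score 4 or 5 with no significant change in FDG uptake from baseline at interim or end of treatment".
- Progressive metabolic disease: a score of 4 or 5 with uptake above baseline, and/or new avid foci.

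**Who is assessed by PET.** Section 6.6 says: "Positron emission tomography-computed tomography should be used in subjects with FDG-avid tumor histology". Histologies of low or variable avidity go to CT or MRI, and the five-point scale (5PS) is assigned to avid histologies.

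**Entry.** Inclusion criterion 6 reads: "Have bi-dimensionally measurable disease by Lugano Classification for NHL". Its limits are on size only: longest diameter above 1.5 cm for nodes and above 1.0 cm for extranodal disease.

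**The concern.** A response category should record a change from baseline. Partial metabolic response, no metabolic response and uptake-based progression all refer to baseline uptake. Complete metabolic response does not. A subject can enter on lesion size alone with a scan that already scores 1-3. That subject then meets the response rule at the first follow-up scan even if nothing has happened.

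The error runs in one direction and falls in the most favorable category. It would raise ORR, BORR and the CR rate. Under SAP 6.1.3, which admits subjects with CR to the duration analysis, it would also add subjects whose response has no real start date. No check is certain to catch it: the study is open-label, response is assessed locally, and central review under 6.6.1 takes place only if the sponsor considers it necessary.

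**Working it through.** The plan contains no figure that rests on this rule, and section 7.3 states that no power calculation is made. The check is therefore mainly a reading of the categories, followed by a range for the size of the effect.

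**Step 1. Classify a subject with baseline score 1-3, an unchanged score at follow-up, no new lesions and no avid marrow disease.**

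| PET category (Table 12) | Follow-up score needed | Compared with baseline? | Does the subject fit? |
|---|---|---|---|
| Complete metabolic response | 1-3 | No | Yes |
| Partial metabolic response | 4-5 | Yes, reduced uptake | No |
| No metabolic response | 4-5 | Yes, no significant change | No |
| Progressive, by uptake | 4-5 | Yes, increased uptake | No |
| LYRIC indeterminate | not stated | Yes, increase in uptake or size | No |

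Only complete metabolic response is left. Table 13 has a not-evaluable code, but nothing links it to low uptake at baseline.

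**Step 2. Classify the same subject by the CT/MRI column.** CR there requires target nodes to shrink to 1.5 cm or less, and PR requires a fall of at least 50% in the sum of products. An unchanged subject is stable disease. The two columns give opposite answers for the same subject.

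**Step 3. Who can reach this cell.** The subject must be assessed by PET, through an avid histology or through a PET scan despite low or variable avidity. The 5PS is one score for the most avid area across all index and non-index lesions (Appendix 3), so the whole baseline scan must score 1-3. Low uptake in the measurable lesions alone is not enough.

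**Step 4. Size.** The share f of such subjects is not in the documents. It is an assumption, taken from 1% to 10%. Part 2 has up to 40 subjects (3.7).

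- Per subject: 1/40 = 2.5 points. This is an upper value, since a subject who also responds by CT adds nothing.
- Expected number = 40f. Chance of at least one = 1 - (1 - f)^40.

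| Assumed f | Expected number in 40 | Chance of at least one |
|---|---|---|
| 1% | 0.4 | 33% |
| 2.5% | 1 | 64% |
| 5% | 2 | 87% |
| 10% | 4 | 98.5% |

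As an illustration, start from 13/40, close to the 33% ORR that section 1.3.1 cites for lenalidomide plus rituximab (exact 95% intervals):

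- 13/40 = 32.5% (18.6 to 49.1)
- 14/40 = 35.0% (20.6 to 51.7)
- 15/40 = 37.5% (22.7 to 54.2)
- 17/40 = 42.5% (27.0 to 59.1)

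One or two such subjects move the estimate by 2.5 or 5 points, well inside the interval.

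**The case against.** The strongest reply is that section 6.6 already sends low- and variable-avidity histologies to CT or MRI, where an unchanged node cannot be CR. Part 2 takes only DLBCL, including mixed histology. What remains is an avid histology with no disease above score 3 at entry, and the documents do not suggest that such subjects are expected. This stands as a limit on frequency. It does not close the gap: the rule depends on histology and not on the subject's observed uptake, it is worded as a recommendation, and the response definitions in the synopsis, 7.9 and SAP 6.1.1 do not repeat it.

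It can also be said that the opening of SAP 6.1.1 excludes a subject with no shrinkage. But the same paragraph then counts the score by itself, so the SAP contradicts itself and does not resolve the matter.

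A reader might infer three stronger things that the documents do not support:
- *That the bias is largest in Part 1 because all subtypes are allowed there.* The subtypes that set Part 1 apart by avidity are the ones assigned to CT/MRI. One subject does weigh more in a small cohort (1/6 = 16.7 points), but dose decisions rest on DLTs, not on response.
- *That such a response lasts until new avid disease appears.* Table 12 also makes a rise to score 4-5 in an existing lesion progressive metabolic disease, and LYRIC indeterminate response can apply on growth in size.
- *That entry to the duration analysis is certain under the protocol.* Section 7.9 asks for benefit by both response criteria without saying what both means. The SAP wording is clearer, and it admits CR.

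**Conclusion.** The rule is wrong as written. For a subject assessed by PET whose entire baseline scan scores 1-3, the plan records a complete response with no change, against the SAP's own description of ORR. This follows from the text and needs no assumption.

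The size does rest on an assumption, because the documents give no distribution of baseline scores. Each affected subject adds at most 2.5 points to the Part 2 response rate at n = 40, and nothing if that subject also responds by CT. The number affected is probably small. ORR is a descriptive secondary endpoint with no hypothesis test and no dose decision attached, so the effect is minor. The correction is still worth making, because the error can only raise the rate and enters as CR.

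**What to change.** In the synopsis, Protocol 7.9 and SAP 6.1.1, and in a note to Table 12:
1. Score metabolic response only in subjects with a baseline 5PS of 4 or 5.
2. Assess subjects with a baseline 5PS of 1-3 by the CT/MRI column. If there is no baseline CT measurement, the subject is not evaluable for response. Efficacy is summarized on the safety population, so the SAP should say that such a subject stays in the denominator.
3. Define objective response as CR or PR per Table 12, and remove the free-standing score of 1, 2 or 3.

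Step 3 alone would not be enough, because Table 12 already equates a score of 1-3 with complete metabolic response. The baseline condition does the work.

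The cost is wording. Appendix 3 assigns a 5PS to each PET/CT scan in the study, and section 6.6 already asks for diagnostic-quality CT at baseline whenever possible. ORR may come out slightly lower, and an occasional subject without a baseline CT will be not evaluable.

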⁴ Prior medication is any medication (prescription, OTC and supplements) used within 4 weeks prior to the start of treatment. Prior therapy for NHL should be captured separately from prior medications.

⁵ Prior systemic therapy for NHL (including SCT) administered at any time before the start of treatment should be documented by itemizing each regimen (line of treatment) and the individual agents within each regimen. The date of last CD20-based therapy should also be documented in the CRF.

⁶ Prior radiotherapy for NHL administered at any time before the start of treatment.

⁷ Blood pressure (systolic and diastolic), heart rate and respiratory rate should be measured after 5-10 minutes of quiet rest in a sitting or semi-recumbent position.

⁸ When ECG and blood pressure assessments are scheduled to occur at the same time point, then the ECG should be performed first and the blood pressure/heart rate measurement may begin immediately after ECG recording (without additional 5-10 minutes' rest).

⁹ Triplicate 12-lead ECG should be obtained as three standard ECGs recorded in close succession and not more than 2 minutes apart. The subject must rest quietly in supine or semi-recumbent position for 5-10 minutes before and during the procedure.

¹⁰ A scan of all anatomic regions involved with the measurable disease by PET-CT (in subjects with FDG-avid tumor histology) or CT/MRI (in subjects with tumor histology of low or variable FDG avidity). CT of diagnostic quality should be collected for all subjects at baseline, whenever possible.

¹¹ Screening (baseline) radiological tumor assessments should be obtained as close to the start of treatment as possible, and within 28 days of C1D1.

¹² Done at Screening (within 1 month before starting study treatment). A pre-study LVEF assessment is acceptable if obtained within 6 months before screening and at least 28 days after the last cancer therapy provided the subject has not received any potentially cardiotoxic agents since then.

¹³ It is recommended to assess RTX serum concentration prior to performing other screening procedures.

¹⁴ Calculated by the central laboratory using the Cockcroft-Gault equation and the serum creatinine from the corresponding chemistry panel.

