¹A score of 3 in many subjects indicates a good prognosis with standard treatment, especially if at the time of an interim scan. However, in trials involving PET where de-escalation is investigated, it may be preferable to consider a score of 3 as inadequate response (to avoid undertreatment). Measured dominant lesions: Up to six of the largest dominant nodes, nodal masses, and extranodal lesions selected to be clearly measurable in two diameters. Nodes should preferably be from disparate regions of the body and should include, where applicable, mediastinal and retroperitoneal areas. Non-nodal lesions include those in solid organs (e.g., liver, spleen, kidneys, lungs), gastrointestinal involvement, cutaneous lesions, or those noted on palpation. Nonmeasured lesions: Any disease not selected as measured, dominant disease and truly assessable disease should be considered not measured. These sites include any nodes, nodal masses, and extranodal sites not selected as dominant or measurable or that do not meet the requirements for measurability but are still considered abnormal, as well as truly assessable disease, which is any site of suspected disease that would be difficult to follow quantitatively with measurement, including pleural effusions, ascites, bone lesions, leptomeningeal disease, abdominal masses, and other lesions that cannot be confirmed and followed by imaging. In Waldeyer's ring or in extranodal sites (e.g., gastrointestinal tract, liver, bone marrow), FDG uptake may be greater than in the mediastinum with complete metabolic response, but should be no higher than surrounding normal physiologic uptake (e.g., with marrow activation as a result of chemotherapy or myeloid growth factors).

²See original paper ([Cheson 2014](#), [Cheson 2016](#)) for more detailed information on immune related response.

Lugano 5PS range ([Cheson 2014](#))

The 5PS ranges from a score of 1 (where no uptake is discernible in the lesion) to a score of 5 (where the uptake in the lesion is markedly increased compared to the uptake in the liver parenchyma). A single 5PS score, which represents the most FDG-avid (i.e., metabolically intense) area of disease (across all index and non-index lesions), is assigned for each PET/CT scan in the study, see Table 13.

Table 13: Modified Lugano 5-point scale (5PS)

Score	Description
1	No uptake
2	Uptake \leq mediastinum
3	Uptake $>$ mediastinum but \leq liver
4	Uptake moderately increased above liver at any site

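### Section 6.6 and Table 2 note 10 require scans only of regions with measurable disease, so disease elsewhere need not be imaged and Appendix 3 cannot be fully applied

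*Protocol*

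**What the plan says.** **Screening.** Protocol Table 2, note 10: "A scan of all anatomic regions involved with the measurable disease by PET-CT (in subjects with FDG-avid tumor histology) or CT/MRI", the CT/MRI option being for histologies of low or variable avidity.

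**Response assessments.** Section 6.6 sets the same extent: "Efficacy of the study drugs (tumor response) will be assessed by the scan of all anatomic regions involved with the measurable disease". It adds: "The same technique (e.g. slice thickness, field of view) should be used for all scans during the study treatment period".

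**Response criteria.** Appendix 3, Table 12 lists among the CT/MRI grounds for progression "A new node >1.5 cm in any axis", with no restriction to regions involved at baseline. For PET, the text before Table 13 assigns "A single 5PS score, which represents the most FDG-avid (i.e., metabolically intense) area of disease (across all index and non-index lesions").

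**Elsewhere.** Section 7.9 adds CT or MRI alongside PET where possible, in order to obtain measurements, and says nothing on extent. SAP Section 7.2 and its subsections refer to Lugano with LYRIC and add no coverage rule.

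**The concern.** Lugano response is a statement about all of a subject's lymphoma. Measurable lesions supply the size change, but the category also depends on what has happened to non-measured disease and on whether anything new has appeared. If the required scan stops at the regions that hold measurable disease, a site can follow the protocol exactly and lack the data to complete Table 12.

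At stake are objective response, DOR and PFS, which are secondary endpoints, and the DCR defined in Section 7.9. The synopsis names efficacy among the purposes of Part 2, and there is no control arm in which the same error would occur and cancel out.

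**Working it through.** No figure in the plan depends on scan extent, so this is a comparison of text. The required scan is set against each element of Appendix 3, Table 12 that reaches beyond measured lesions.

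| What Table 12 asks | Can the minimum scan answer it? |
|---|---|
| CR and PR, both modalities: no new lesions | Only within the scanned regions |
| CR on CT/MRI: non-measured lesions absent, no extralymphatic disease | Only within the scanned regions |
| PD: a new node, new extranodal site, new FDG-avid focus, or progression of non-measured disease | Only within the scanned regions |
| LYRIC indeterminate response: less than 50% growth in SPD with a new lesion | Only within the scanned regions |
| 5PS: the hottest area over index and non-index lesions | Only if every non-index lesion lies in a scanned region |

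**Can relevant disease lie outside those regions?** Yes. The notes to Table 12 count bone lesions, effusions, ascites and leptomeningeal disease as non-measured, and none of these has to share a region with a measurable lesion. Exclusion criterion 2 also admits some subjects with treated, stable brain or spinal disease.

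**Does the baseline scan establish which regions are involved?** Not by itself. The scan is defined by the involved regions, but no broader imaging is required to find them. Section 6.1.4 asks for stage at screening, and Appendix 2 separates stage II from stage III by disease on both sides of the diaphragm. No scan is specified to support that.

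**Does later imaging widen the view?** The constant-technique sentence in 6.6 favors carrying the baseline field of view forward. Where a later scan does extend further, as an unscheduled scan might, or as radiology taken from medical records in long-term follow-up might (Section 3.5), a lesion already present but not imaged at baseline can be read as new.

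**Direction.**
- An unseen new or persisting lesion moves a call toward CR, PR or SD and delays progression. ORR, BORR and DCR rise; DOR and PFS lengthen.
- An old lesion first seen on a later, wider scan moves the call the other way.

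The first is the main risk under the text as written, because the second needs a departure from the constant field of view.

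**Size.** The documents give no rate of disease outside measurable regions. One false responder among 40 subjects in Part 2 adds 1/40 = 2.5 percentage points to the response rate; how many there would be is unknown.

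For PFS, only an illustration on assumed inputs is possible. Assume:
- exponential PFS with median 3.7 months, about 112.6 days (the figure Section 1.3.1 gives for lenalidomide plus rituximab);
- scans at about Day 54 and then every 56 days;
- a fraction p of events found late.

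Then S(t) = exp(−ln 2 × t/112.6), so S(54) ≈ 0.717 and S(110) ≈ 0.508. Just after the second scan, the proportion called progression-free is:
- one scan late: 0.508 + p × (0.717 − 0.508). This gives 0.529 at p = 0.1 and 0.550 at p = 0.2.
- two scans late: 0.508 + p × (1 − 0.508). This gives 0.557 at p = 0.1 and about 0.61 at p = 0.2.

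Both p and the delay are invented. The formula also delays deaths, which would in fact be recorded on time. These values are an upper-side illustration, not an estimate.

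**The case against.** The best defense is that the text sets a floor. Nothing forbids a wider scan, and many sites may do one as routine. New lesions inside the scanned regions are seen. Around the floor there are safeguards:
- Unscheduled scans "may be ordered at the investigator’s discretion". They generally need a prior suspicion, so they do not replace scheduled coverage.
- Section 6.6 also says "Scans must meet the SOC for imaging of lesions in the respective organ system(s"). This concerns the quality of lesion imaging by organ system and not how much of the body is scanned.
- Nodes and abdomen are examined on Day 1 of each cycle (Section 6.2.3). That cannot be relied on for deep nodes or small extranodal lesions.
- Without PET/CT, CR is to be confirmed by marrow biopsy (Section 6.9). That checks marrow only.
- Central review (Section 6.6.1) is optional and cannot read what was not scanned.
- Ann Arbor staging implies some knowledge of the whole body at entry, but no imaging is tied to it and it is not repeated at response assessments.

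These reduce the gap without closing it. The defense does rule out three stronger readings that a reader might infer:

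1. *Disease elsewhere is never imaged.* The text supports only that it need not be.
2. *Every unseen new lesion is a missed progression.* Table 12 lists a new lesion with less than 50% growth in SPD as LYRIC indeterminate response, so it would not automatically be PD even with full coverage. The point about CR and PR is unaffected, since both require no new lesions.
3. *The bias can only flatter the drug.* A narrow baseline followed by a wider scan can produce false progression.

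**Conclusion.** The coverage wording in Section 6.6 and Table 2 note 10 does not fit Appendix 3. A site that follows the minimum exactly may be unable to establish the absence of new lesions that CR and PR require, to confirm the other conditions for CR on CT/MRI, to assign the 5PS over all lesions, or to detect new disease that counts toward PD or indeterminate response. This follows from the text and needs no numerical assumption.

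The likeliest effect is overstated response and disease control and prolonged DOR and PFS, with a smaller possibility of error the other way. Sites that image more widely would in effect apply a stricter standard than sites that keep to the minimum.

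The size cannot be estimated from the documents, and the PFS illustration should not be quoted as a measure of bias. A reader might also infer that the trial's main conclusions are at risk. They are not: the primary endpoint is adverse events and DLTs, the MTD rests on DLTs, and the affected endpoints are descriptive with no power calculation behind them. It is still worth correcting before Part 2 baseline scans, because a region not imaged at baseline cannot be recovered later.

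**What to change.** In Section 6.6 and Table 2 note 10, replace the coverage wording with one stated minimum that is the same at screening and at every assessment and is sufficient to judge new and non-measured disease under Appendix 3. For example: whole-body PET-CT for FDG-avid histology; otherwise CT/MRI of neck, chest, abdomen and pelvis plus any other known site. Keep the constant-technique sentence, which then preserves adequate coverage.

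Record the extent of each scan and flag in the response data any timepoint with less than the minimum, so that CR and PR calls on incomplete imaging can be identified. A flag is enough; no new scoring rule need be added to Table 12.

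Cost: wording in two places, one data item, and no added visit. Sites that would have limited the scan need a longer field of view, with slightly more scan time and CT radiation. Where MRI is used, the examination is longer.
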